Amongst the risk factors are maternal age, obesity, medical disorders such as antiphospholipid syndrome, hypertensive disorders, renal diseases diabetes mellitus and previous PET. A history of PET increases the risk of recurrence 7 fold and this is compounded by GA at delivery for the affected pregnancy (3,4). Moreover, both chronic hypertension and pre-existing diabetes increase the risk of PET which is further enhanced by the degree of glycemic control (5,6). Interestingly maternal and paternal history of diabetes and hypertension have been associated with increased risk of PET (7). Additionally, maternal age > 40 years and pregnancy interval > 10 years increases the risk of PET by two to three folds respectively (8,9). A BMI > 35 increases the risk of PET by 4 folds in both multiparous and nulliparous women (3,10). Moreover, assisted reproduction techniques and multiple gestation have also been associated with increased risk of PET (11). A combination of diabetes and obesity, which has a high prevalence in Qatar, significantly increases the risk of PET. Despite these risk factors only a fraction of those with at high risk eventually develop PET as the current criteria for prediction is not specific.

Various measures to predict, prevent and treat pre-eclampsia have been investigated and tried by several groups/researchers (12). However, these have not been very successful, primarily because PET is a disease of theories with an unclear primary pathophysiology and thus no clear target for either these predictive tools or interventions. Evidence, however, does suggest that in patients at risk of developing PET there is inadequate trophoblastic invasion, placental hypo-perfusion, and endothelial cell activation (13–15). This the basis for the most widely non-invasive clinical tool of Doppler velocimetry of the uterine artery; but again, this has a poor sensitivity (16,17).

An imbalance in pro-angiogenic factors such as vascular endothelial growth factor (VEGF) and placental growth factor (PIGF) (decreased) and antiangiogenic factors such as soluble FMS-like tyrosine kinase -1 (sFlt-1) (increased) has been implicated for the inadequate remodeling of spiral arteries (which is essential for the maintenance of a normal placental perfusion) in those who develop PET (18,19).

Vascular endothelial growth factor (VEGF) is an important signaling protein in health and diseases such as cancer, kidney diseases and PET (20). The VEGF family is composed of five members and three tyrosine kinase receptors. The signaling proteins are: VEGFA, VEGFB, VEGFC, VEGFD and placental growth factor (PIGF) (reviewed in (20)). The receptor tyrosine kinase consists of VEGFR1 (also known as Flt-1), VEGFR2 and VEGF3, with different binding capacity to VEGF proteins (20,21). A soluble Fms like tyrosine kinase-1 (sFlt-1) a truncated form of VEGFR1, has also been identified which lacks the VEGFR1 cytosolic domain (22). In addition to ligand binding, VEGFR has been shown to be activated through non-ligand binding and mechanical forces (23–25). VEGF proteins are upregulated under hypoxic conditions such as PET, growth factor signaling and by hormones such as estrogen (20).

PET is characterized by a hypoxic environment, resulting in considerable changes in maternal leukocyte gene expression, altered expression of the VEGF signaling pathway and AMP-activated protein kinase (AMPK) and secretion of sFlt-1 into the maternal circulation (26–31). VEGF including PIGF has been identified as a crucial in the signaling pathway for angiogenesis and vasculogenesis during placental development (32–35). Indeed, deletion of a single VEGF allele in mice resulted in embryonic lethality due to immature angiogenesis (36,37). The invasion of maternal spiral arteries by cytotrophoblasts is vital for adequate oxygen and nutrient supply (14,38–40). This process is believed to be mediated by binding of VEGF and PIGF to Flt-1 (40). Further, fetal DNA variants at the Flt-1 region has been associated with PET and reported recently (59). However, the pathophysiology of PET is still unclear and understanding of its molecular mechanism is warranted.

A decreased level of VEGF and PIGF free form has been observed that has been attributed to their blockade by the increased level of sFlt-1 in pre-eclamptic women (29,41,42). Indeed, the introduction of sFlt-1 to a pregnant rat led to hypertension and proteinuria similar to that seen in PET women (42). Furthermore, an altered ratio of serum PIGF/sFlt-1 has been found to be associated with PET diagnosis and disease severity (43–46). Indeed, there is now a drive to use this ratio in screening women at risk of PET but most of the data were generated in late pregnancy rather than in early pregnancy – a time when interventions have been shown to have maximum impact (46). It would seem from this greater understanding of the underlying physiological changes in women that develop PET that any interventions that have the potential to alter this milieu are more likely to be successful.

Very recently a double-blind, placebo-controlled trial, that randomly assigned pregnant women without diabetes who had a body-mass index of more than 35 to receive metformin, at a dose of 3.0 g per day, or placebo (225 women in each group) from 12 to 18 weeks of gestation until delivery showed a significant reduction in the incidence of PET in those who received metformin (47). Since metformin is now frequently prescribed to obese type II diabetic women and gestational diabetics with poor glycemic control on diet, it is hypothesized in those at risk of PET, metformin will not only reduce the incidence of PET but will modify the PIGF/s-Flt-1 ratio in favor of normal pregnancies.

2. Study aims and goals

Aim 1: To investigate whether the administration of metformin to women at high risk of pre-eclampsia will reduce the incidence.

Aim 2: To determine accuracy of the ratio of PIGF/sFlt-1 in predicting PET and the effect of metformin on this ratio

Aim 3: To study the molecular mechanisms and signaling pathways associated with increased levels of sFlt-1 and PET

3. Objectives of this study

Aim 1: To investigate whether the administration of metformin to women at high risk of pre-eclampsia will reduce the incidence.

The objectives under this aim will include

1. A comparison of the incidence of pre-eclampsia and its severity in women receiving metformin versus standard care,
2. A comparison of the GA at delivery, maternal and fetal outcomes in those receiving Metformin versus standard care,
3. A comparison of the timing of onset of PET between the two groups and

Aim 2: To determine accuracy of the ratio of PIGF/sFlt-1 in predicting PET and the effect of metformin on this ratio

The objectives under this aim will include,

1. A comparison of the serum levels of the PIGF/sFlt-1 ratio measured in early pregnancy between non-PET and PET patients.
2. A comparison of the PIGF/sFlt-1 ratio PET in patients who received metformin versus standard care group.

Aim 3: To study the molecular mechanisms and signaling pathways associated with increased levels of sFlt-1 and PET.

Regarding aim 3: in response to the reviewer's comments, the study team has agreed to collect the blood sample and placenta from the patients and store them for future analysis.

4. Preliminary data or studies

Metformin safety in pregnancy

substantial evidence on the benefits of metformin an antihyperglycemic agent when pregnant women with gestational and Type 2 diabetes. In polycystic ovary syndrome

1 Jan - Revised On May 2017

Page 5 of 22

(PCOS) patients, it is known to decrease the risk of first trimester miscarriages and the incidence of gestational diabetes (48,49). In diabetic pregnancies, metformin has been associated with favorable maternal and neonatal outcomes (50,51). Observed maternal outcomes include less weight gain during pregnancy, better glycemic control, and reduced fat distribution (52). Other benefits include a reduction in pregnancy induced hypertension and PET, lower risk of neonatal hypoglycemia and ICU admission. Neonatal outcomes include: reduced fat around organs, which could result in improved insulin resistance and prevention of diabetes later in life (52). Even though metformin is known to cross the placenta, its use in early pregnancy or late pregnancy has not been shown to be associated with an increased risk of congenital malformation or adverse neonatal outcomes except a lower neonatal birth weight (53–56).

Metformin has been safely administered at the dose we propose to use here to diabetic patients. It has become the first line treatment of type 2 DM in pregnancy and poorly controlled gestational diabetes on diet based on the NICE guideline and the national diabetes guideline in Qatar. However, anticipated side effects include: GI disturbances such as gas (4-12%), heartburn, stomach pain (3-4%), nausea (7-9%), and GI changes. Serious side effects associated with its use are hypoglycemia and lactic acidosis which are extremely rare (<1%) (57).

Metformin in PET:

Recently data are emerging on reduced incidence of gestational hypertension and pre-eclampsia with metformin use in pregnant patients with diabetes, PCOS or obese non-diabetic patients (58). In a prospective study of pregnant PCOS women, metformin was shown to be associated with a significant reduction in the incidence of gestational hypertension (54). A randomized double-blinded placebo controlled trial of obese pregnant women without diabetes on metformin, showed a 75% reduction in the incidence of pre-eclampsia (47). A recent systematic review and meta-analysis concluded that metformin is associated with a lower incidence of pre-eclampsia in women with gestational diabetes mellitus or Type 2 diabetes (59), emphasizing its potential role in the prevention of PET. However, it concluded that robust evidence is still lacking and randomized control trials (RCT) are needed. Furthermore, there have been no such studies in our local GCC population to the best of our knowledge.

Therefore, we would like to conduct this RCT to explore the role of metformin in the prevention of PET. Pre-eclampsia is considered a multisystem and complex disease with no definite preventive or treatment measures other than delivery or termination of pregnancy. The use of metformin if confirmed to be effective will therefore not only significantly decrease the maternal and fetal morbidity and mortality associated with pre-eclampsia but also a significant decrease in the health care expenditure. Indeed, there are no randomized control trials (RCT) that specifically investigated the use of Metformin for the prevention of PET. Since metformin reduces the gestational weight gain, it follows that it would most likely reduce incidence of PET

^{60, 75} Effect of metformin on maternal and fetal outcomes in obese pregnant women

(EMPOWaR) trial showed no effect but timing of the intervention (introduction of metformin was much later in pregnancy) (61).

Metformin has been in use since 1957 but its specific mechanism of action is unknown (62). Previously, AMPK-activation has been identified as one of the mechanisms by which it exerts its angiogenic activity (63). However, metformin does not activate AMPK directly. Instead, AMPK activation is a result of metformin inhibition of the mitochondrial respiratory chain complex 1 (reviewed in (64,65)). Apart from diabetes, it has also been implicated in the prevention of cancer, adverse outcomes in women with PCOS and most recently in the prevention of PET (reviewed in (66)). In an ex-vivo study using primary placental tissue from PET placentas, metformin treatment resulted in reduced endothelial dysfunction, enhanced vasodilatation and induced angiogenesis by sFlt-1 and endoglin reduction possibly at the mitochondrial level (30). Despite these, the exact mechanism behind its role in the prevention of PET remains poorly understood. Further clarification of how metformin decreases the incidence of pre-eclampsia needs to be examined. Here we plan to explore altered maternal serum levels of sFlt-1, PIGF and VEGF in pregnant women using metformin.

5. Study design and methodology

This is an open label, randomized control trial (RCT) in which high risk for pre-eclampsia pregnant subjects will be randomly assigned to either an intervention group (metformin 1 gm twice daily plus aspirin 100 mg per day and standard of care) versus control group (aspirin 100 mg per day and standard of care) that will be administered between 11^{+0} to 13^{+6} weeks of gestation until delivery (appendix 1). Only women at high risk of pre-eclampsia as defined by the ACOG practice bulletin will be included (see inclusion criteria). Patient assignment will not be blinded as control group will not be given a placebo; the data will be analyzed on an intention to treat basis. Enrolled subjects will be followed throughout pregnancy and up to 30 days post-delivery (as per hospital practice).

Study definitions:

High risk of preeclampsia:

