Systolic blood pressure of 160 mm Hg or more, or diastolic blood pressure of 110 mm Hg or more on two occasions at least 4 hours apart (unless antihypertensive therapy is initiated before this time), Thrombocytopenia (platelet count less than $100,000 * 10^9/L$), Impaired liver function as indicated by abnormally elevated blood concentrations of liver enzymes (to twice the upper limit normal concentration), and severe persistent right upper quadrant or epigastric pain unresponsive to medication and not accounted for by alternative diagnoses, Renal insufficiency (serum creatinine concentration more than 1.1 mg/dL or a doubling of the serum creatinine concentration in the absence of other renal disease), Pulmonary edema
 New-onset headache unresponsive to medication and not accounted for by alternative diagnoses, Visual disturbances

Study population:

Patient characteristics:

Participants who will be included in this study are pregnant women who are at high risk for developing pre-eclampsia as defined by the ACOG practice bulletin (for review (67)).

Inclusion criteria:

To be eligible to be included in the study, a woman has to have all of the following; Confirmed y, gestational age $< 12^{+0}$ weeks, live fetus at time of booking ultrasound scan

(between 11⁺⁰ and 13⁺⁶ weeks of gestation), and to be considered as high risk of preeclampsia. According to ACOG (67), pregnant women are considered high risk of preeclampsia if they showed at least one of the following; History of preeclampsia, especially when accompanied by an adverse outcome, Multifetal gestation, chronic hypertension, Type 1 or 2 diabetes, Renal disease, Autoimmune disease (ie, systemic lupus erythematosus, the antiphospholipid syndrome), OR more than one of the following: Nulliparity, Obesity (body mass index greater than 30), Family history of preeclampsia (mother or sister), Sociodemographic characteristics (African American race, low socioeconomic status), Age 35 years or older, Personal history factors (eg, low birth weight or small for gestational age, previous adverse pregnancy outcome, more than 10-year pregnancy interval)

Exclusion criteria:

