Age under 18 years, hyperemesis gravidarum, unable to sign the consent form, type 1 or 2 diabetes mellitus, early gestational diabetes, auto-immune disease, fetal abnormality identified at time of scanning (between 11⁺⁰ and 13⁺⁶ weeks of gestation), bleeding disorder, peptic ulcer, hypersensitivity to aspirin or metformin, long use of NSAIDS before initiation of intervention, contraindication to metformin or aspirin and participation in another concurrent trial.

Study sites:

The study will be conducted at the Women Wellness and Research Center (WWRC), Doha, Qatar. Patient will be identified from three Primary Health Centers. There will, however, will be very few volunteers who will have all their visits and tests done at the WWRC with the health center facilitating their identification only.

Study methods:

Patient identification and randomization

If the primary physician in the Primary Health Center or the main center identifies a potential candidate for the study based on the inclusion and exclusion criteria, he/she will inform the patient about the study and document her willingness to participate in the study in the electronic medical record to avoid cold calling and according to HIPAA recommendations. The investigator of the respective site will then be contacted through email by the primary physician.

the patient will be contacted by the study investigator and arrange an appointment in the WWRC to inform her about the study and if she accepted to participate, give her the patient information leaflet (PIL) and then obtain informed consent once all her questions have been answered.

Each center has one coordinator, who will be responsible in conjunction with the investigator for recruitment, clinical interviews, determining eligibility and obtaining signed informed consent forms. After successful screening, eligible pregnant women will be randomly assigned to either intervention or control group. Random sized blocks of 4 or 6 will be computer generated with 1:2 ratio.

Sample isolation and laboratory studies (appendix 2):

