- (c) At delivery data to be collected will include gestational age at admission, vital signs, indication for delivery, type of delivery, compliance with protocol, blood for CBC, LFT, and the biomarkers of interest. Post-delivery, discharge vitals, antihypertensive treatment on discharge will be collected.

(d) Exit interview: patient will be called to check for any relevant ADR.

8. Data Management and Analysis plan

Data management:

Upon randomization, research coordinators will be responsible for data collection using approved CRFs. To maintain patient confidentiality, study document such as signed informed consent, and CRFs will be stored in locked cabinets, excel file containing patient identifiable information will be password protected, and all data including patient clinical information and research laboratory results will be entered into the clinical trial management software using patient generated study ID number.

Data analysis:

Descriptive data: Numerical data will be presented as mean and standard deviation where normally distributed or median and range where it's not normally distributed. Categorical data will be presented as frequency and percentages. The percentage of women developed PET will be compared between the intervention and control group using chi square test.

Quantitative data between two arms will be analyzed using either "Unpaired t test or Mann Whitney U test depending on normality of the data distribution". Also, outcomes measured at different time points should be statistically analyzed both within and between groups using repeated measure ANOVA statistical method followed by appropriate multiple comparison tests. All P values presented will be two-tailed. A multivariate logistic regression will be employed to assess the association between metformin use and PET adjusting for confounding factors such as patient demographics (age, GA at delivery, history of risk factors of PET\mentioned above) and co-morbidities such as DM, the dose of metformin, the need to use of antihypertensive drugs, including duration of treatment and any other medications. P values <0.05 will be considered as statistically significant. All Statistical analyses will be done using statistical packages SPSS 22.0 (SPSS Inc. Chicago, IL) and Epi-info (Centers for Disease Control and Prevention, Atlanta, GA) software.

9. Anticipated results and evaluation criteria

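### Multifetal pregnancies are eligible and fetal outcomes are compared by arm, but Section 8 fixes neither the unit of analysis nor a method for siblings; a per-baby analysis with the listed tests would understate standard errors

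*SAP*

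**What the plan says.** - **Objective.** Section 3, Aim 1, objective 2 is "A comparison of the GA at delivery, maternal and fetal outcomes in those receiving Metformin versus standard care". It names no fetal outcome and no unit of analysis.
- **Eligibility.** Section 5 (Study definitions and Inclusion criteria) admits a woman with "at least one of the following; History of preeclampsia, especially when accompanied by an adverse outcome, Multifetal gestation, chronic hypertension", among other factors, so a multifetal pregnancy qualifies by itself.
- **Exclusions.** Two other factors from that list are removed, in the run "type 1 or 2 diabetes mellitus, early gestational diabetes, auto-immune disease, fetal abnormality identified at time of scanning". Multifetal gestation is not removed.
- **Tests.** In Section 8 (Data analysis), quantitative data are compared between arms by "Unpaired t test or Mann Whitney U test depending on normality of the data distribution". For PET, "The percentage of women developed PET will be compared between the intervention and control group using chi square test".
- **Other methods in Section 8.** For repeated measurements, "outcomes measured at different time points should be statistically analyzed both within and between groups using repeated measure ANOVA". A logistic model relates metformin use to PET with adjustment for confounders. Neither deals with babies of the same mother.
- **Level.** "All P values presented will be two-tailed", with significance below 0.05.

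**The concern.** Babies of one mother share the allocated arm, the gestational age at delivery and the intrauterine environment, so their outcomes are positively correlated. An unpaired t or Mann-Whitney test that takes each baby as a separate observation counts that shared information twice. Confidence intervals are then too narrow and the test rejects more often than 5%.

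Plurality adds to this for outcomes that differ on average between twins and singletons. If the number of twin pregnancies differs by chance between arms, each extra pair pulls that arm's mean by two correlated values. The logistic model adjusts for PET risk factors, but it applies only to PET and does not reach the fetal outcomes.

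At stake are the secondary comparisons in which a benefit or harm to the baby would be sought. Section 4 itself notes lower birth weight with metformin, an outcome measured per baby. Because the unit is open, it could also be chosen after the data are seen, between a valid analysis and an anti-conservative one.

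**Working it through.** **1. The plan's own figure.** Section 6 gives PET rates of 11.3% and 3%, 80% power, 5% significance, 172 per arm, and 207 after a 20% allowance.

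- Uncorrected: n = [1.96·√(2·0.0715·0.9285) + 0.8416·√(0.113·0.887 + 0.03·0.97)]² / 0.083² = 150.1, so 151 per arm.
- With continuity correction: (150.1/4)·[1 + √(1 + 4/(150.1·0.083))]² = 173.4, so 174. This is within about 1% of 172.
- Allowance: 172 × 1.2 = 206.4, so 207, as stated.

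PET is counted once per woman, so clustering leaves this calculation unchanged. The 172 per arm is used below.

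**2. Assumptions.** The SAP gives neither the share of twin pregnancies (t) nor the within-pair correlation (ρ). I take t = 2% to 30% and ρ = 0.5 to 0.7. Higher-order multiples are ignored.

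**3. Per-baby analysis, twins and singletons with the same mean.** Of all babies, a share 2t/(1+t) are twins, each with one correlated sibling. Hence:

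- design effect D = 1 + ρ·2t/(1+t)
- proportion by which the naive standard error is too small = 1 − 1/√D
- true two-sided error = 2·[1 − Φ(1.96/√D)]

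| t | D (ρ = 0.5 / 0.7) | SE too small by | True error |
|---|---|---|---|
| 2% | 1.020 / 1.027 | 1.0% / 1.3% | 5.2% / 5.3% |
| 5% | 1.048 / 1.067 | 2.3% / 3.2% | 5.6% / 5.8% |
| 10% | 1.091 / 1.127 | 4.3% / 5.8% | 6.1% / 6.5% |
| 20% | 1.167 / 1.233 | 7.4% / 10.0% | 7.0% / 7.8% |
| 30% | 1.231 / 1.323 | 9.9% / 13.1% | 7.7% / 8.8% |

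Example, t = 10%, ρ = 0.5: D = 1 + 0.5·0.2/1.1 = 1.091; √D = 1.044; 1.96/1.044 = 1.877; error 6.1%.

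Simulated t tests on babies (172 pregnancies per arm, no treatment effect, 20,000 runs per setting) agree within simulation error of a few tenths of a point: about 5.1–5.7% at 2–5% twins, 6–7% at 10%, 7–8% at 20% and 8–9% at 30%.

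**4. Per-baby analysis, twins 1.5 SD lower, twin number varying by chance.** The 1.5 SD is also an assumption, meant for an outcome such as birth weight. Simulated error is about 6–7.5% at 2–5% twins, 8–8.5% at 10%, and 9–10% at 20–30%.

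**5. One value per pregnancy.** Using the mean of the babies with the same unadjusted t test, simulated error was about 4.7–5.5% across all settings, including those in step 4. The listed tests are valid on that unit.

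**6. Gestational age at delivery.** There is one value per woman, so there is no clustering, and randomisation makes the unadjusted comparison valid. Adjusting for plurality removes the variance 1.5²·t(1−t), relative to a within-group variance of 1:

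- t = 5%: 2.25·0.05·0.95 = 0.107; 1 − 1/√1.107 = 5% smaller standard error.
- t = 20%: 2.25·0.20·0.80 = 0.36; 1 − 1/√1.36 = 14% smaller standard error.

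**The case against.** The strongest reply is that the SAP never says babies will be analysed as independent. A reader might infer that from the choice of tests, but the documents do not support it as a statement of fact. Where Section 8 names a unit it is the woman, Section 6 counts patients, and with one value per pregnancy the listed tests hold their level. This stands, and the point is therefore conditional.

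Further replies, and what remains of each:

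- **No per-baby variable is visible.** Objective 2 names none, the delivery data in Section 7 are maternal or per pregnancy, and the full variable list is in an appendix that is not shown. Birth weight is thus only an illustration. Fetal outcomes are nevertheless a stated between-arm comparison, and Section 8 is where this document chooses its tests.
- **Section 8 lists more than t, Mann-Whitney and chi-square.** True: repeated-measures ANOVA and logistic regression are there too. The first covers time points and the second covers PET, so neither handles siblings. Chi-square is assigned only to PET.
- **Adjusting gestational age at delivery for plurality is a preference.** It is not needed for validity. It is offered below only as a gain in precision.
- **The size depends on assumed twin shares.** It does. At 2–5% twins with equal means the inflation is under one percentage point.

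**Conclusion.** The point holds in conditional form. The plan admits multifetal pregnancies, makes fetal outcomes a between-arm comparison, offers only unadjusted independence-based tests for quantitative outcomes, and leaves the unit and the handling of siblings open. If babies are analysed individually, type I error lies somewhere between barely above 5% and about 9% with equal means, and reaches about 10% if twins also average 1.5 SD lower and their number varies by chance. Where it falls depends on a twin share, a within-pair correlation and a twin–singleton difference that are all assumed here.

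It would be wrong to conclude that the primary result or the sample size is compromised, or that the test of gestational age at delivery is invalid: PET, maternal outcomes and gestational age at delivery have one value per woman. The defect is confined to secondary fetal outcomes. It should be corrected because the correction is cheap and those outcomes bear on safety for the baby.

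**What to change.** Add to Section 8:

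1. For each fetal outcome, state whether the unit is the baby or the pregnancy.
2. Compare per-baby outcomes by arm with GEE (robust standard errors) or a mixed model, with the mother as cluster, adjusted for singleton versus multifetal pregnancy. Alternatively, define one value per pregnancy in advance, such as the mean of the babies or any baby affected, with the same adjustment.
3. Count each woman once for gestational age at delivery and other per-pregnancy outcomes. Adjust gestational age at delivery for plurality, described as a precision gain and not as a correction.

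The cost is a few sentences and standard procedures, with no change to recruitment, sample size or conduct. Clustering makes confidence intervals for per-baby outcomes slightly wider than the naive ones. On the figures above, the naive standard error is too small by 1–6% at 2–10% twins and by 7–13% at 20–30%.
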